## 7.2.1 Partial Dates for Adverse Events

If the AE start date is partial or missing, then:

- If AE start date is completely missing, then the AE is considered as treatment-emergent.
- If both AE start month and day are missing and AE start year is the same or after the first dose year, then the AE is considered as treatment-emergent.
- If AE start day is missing and AE start year and month are the same or after the first dose year and month, then the AE is considered as treatment-emergent.

#### 7.2.2 Partial Dates for Concomitant Medication

For medications with incomplete dates, imputation will be used to convert to a complete date. Imputed dates will be used to determine Study Day.

Partial medication start dates will be imputed as follows:

- 1. Only the year is reported: If the subject started to receive study drug in the year reported, then the date of the first dose of study drug will be used as the starting date of the medication. Otherwise, January 1 will be used as the start of the medication.
- 2. The month and year are reported: If the subject started to receive study drug during the month and year reported, then the date of first dose of study drug will be used as the starting date of the medication. Otherwise, the first day of the month will be used as the start of the medication.

Partial medication end dates will be imputed for non-ongoing medications as follows:

1. Only the year is reported: If the subject stopped to receive study drug in the year reported, then the date of the last dose of study drug will be used as the end date of the medication. Otherwise, December 31 will be used as the end of the medication.

2. The month and year is reported: If the subject stopped to receive study drug during the month and year reported, then the date of last dose of study drug will be used as the end date of the medication. Otherwise, the last day of the month will be used as the end of the medication.

If an imputation results in an imputed start date after the stop date, the start date will be set to the day prior to the stop date.

## 7.3 Subject Disposition

Patient disposition information will be summarized by treatment group and in total for ITT set. The number and percentages of patients in safety set and efficacy set will be summarized by treatment group and in total.

The below numbers based on ITT set will be presented in table.

- Number of patients complete all doses of LV305 per protocol
- Number of patients discontinued from LV305 and reason for discontinuation,
- Number of patients complete all doses of G305 per protocol
- Number of patients discontinued from G305 and reason for discontinuation
- Number of patients complete all dose of atezolizumab
- Number of patients discontinued from atezolizumab and reason for discontinuation
- Number of patients receive all doses of CMB305 up to visit 12 based on dose administration page
- Number of patients receive all doses of atezolizumab up to visit 12 based on dose administration page
- Number of patients receive all doses of CMB305 and atezolizumab up to visit 12 based on dose administration page
- Number of patients complete all dose of LV305, G305 and atezolizumab
- Number of patients entered Long Term Follow-Up
- Number of patients completed LTFU Visit (Month 3, 6, 9, 12, 15, 18, 21 >=24)
- Number of patients completed study per protocol
- Number of patients discontinued from study and reason for discontinuation

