#### IMDZ-C232

Abbreviations: AE = adverse event, CT = computed tomography; ECG = electrocardiogram; ECOG = Eastern Cooperative Oncology Group; HepB = hepatitis B; HepC = hepatitis C; HIPAA = Human insurance Portability and Accountability Act; HIV = Human immunodeficiency Virus; meds = medications; mos = months; PBMC = peripheral blood mononuclear cells; SAE = serious adverse event.

- a. A window of ±3 days is permitted for Visits 3 through 12. Follow-up phase visits (Visits 13+) will be permitted a window of ±4 days, Tumor assessments will be permitted a window of ±1 week.
- b. Patients will be followed with visits every 3 weeks (±4 days) for 2 years (from Day 0) for until progression. Tumor size will be assessed every 6 weeks for the first year, then every 12 weeks until progression. Patients will then have no further staging procedures. Tumor biopsies will be obtained at 6 months or longer for patients with treatment response. Tumor biopsies will also be obtained at time of progression.
- c. Informed consent and HIPAA authorization must be signed before any screening study-related procedures are initiated. Three informed consents will be used: one to screen tumor sample for NY-ESO-1, one to engage in the study protocol, and an agreement to continue in the study and obtain peripheral blood samples and biopsies if the patient meets the criteria for progressive disease but wishes to remain on study.
- d. Documentation of NY-ESO-1 expression in prior tumor samples may have been collected from any procedure performed before baseline activities. There is no time limit for use of the results from the IMDZ-approved central lab.
- e. Vital sign measurements include temperature, pulse, respiratory rate, and resting systolic and diastolic blood pressure. On the day of each dosing, vital signs will be obtained pre-dosing and 30 minutes after dosing. For the first atezolizumab infusion, the patient's vital signs (HR, respiratory rate, BP, and temperature) should be measured within 15 minutes of the infusion, during the 60-minute infusion (every 15 [± 5] minutes), and 30 minutes after the infusion. For subsequent infusions, vital signs do not need to be obtained during the infusion if the prior infusion was tolerated without symptoms.
- f. Once the baseline physical exam has been conducted, a simple symptom-directed physical exam should be performed for all subsequent visits. Height and weight will be collected at Day 0 only.

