#### Table 2Schedule of Events – Control Arm

#### Table 2 Schedule of Events – Control Arm

	Screening	Treatment Phase					Mair	itenance	Survival Follow-up n		
Visit	1	2	3	4	5	6	7	8	9	10+	
Timeline – Weeks a	-4 to 0	0	3	6	9	10	12	14	15	Every 3 wks b	Every 3 months (12 wks)
Procedures Timeline – Days	-30 to -1	0	21	42	63	70	84	98	105		
Informed consent/HIPAA c	Х										
Inclusion/exclusion criteria	X										
Demographics/medical history	X										
Tumor-specific therapy history	Х										
NY-ESO-1 expression on pre-study tumor sample screend	X										
Enrollment and randomization		X									
Report AEs and SAEs		X	X	X	X	X	X	X	X	X	X
Record any previous/concomitant medications	X	X	X	X	X	X	X	X	X	X	X
Vital signs e	X	X	X	X	X	X	X	X	X	X	
Physical exam f	X	X	X	X	X	X	X	X	X	X	
ECG (12-Lead)	X								X		
Tumor staging, by CT scan g	X			X			X			X	
ECOG	X	X	X	X	X	X	X	X	X	X	
HIV, HepB, and HepC (5 mL)	X										
Blood for cellular immunity (55 mL)h	X	X		X		X		X			
Blood for safety labs (10 mL)i	X	X	X	X	X		X		X	X	
Thyroid function tests j	X						X			X j	
Urinalysis	X										
Urine sample for pregnancy test k	X	X	X	X	X		X		X	X	
Study drug: atezolizumab		X	X	X	X		X		X	X 	
Tumor biopsy m & b	X			X				Xm		Xb	
Survival Status											X n
Blood volume per visit (mL)	70	65	10	65	10	55	10	55	10		
Total blood volume	70	135	145	210	220	275	285	340	350		

Abbreviations: AE = adverse event, CT = computed tomography; ECG = 12-lead electrocardiogram; ECOG = Eastern Cooperative Oncology Group; HepB = hepatitis B; HepC = hepatitis C; HIPAA = Human insurance Portability and Accountability Act; HIV = Human immunodeficiency Virus; SAE = serious adverse event.

a. A window of ±3 days is permitted for Visits 3 through 9. Follow-up phase visits (Visits 10+) will be permitted a window of ±4 days, Tumor assessments will be permitted a window of ±1 week.

- b. Patients will be followed with visits every 3 weeks (±4 days) for 2 years (from Day 0) for atezolizumab treatment until progression. Tumor size will be assessed every 6 weeks for the first year, then every 12 weeks until progression. Patients will then have no further staging procedures. Tumor biopsies will be obtained at 6 months or longer for patients with treatment response. Tumor biopsies will also be obtained at time of progression.

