# 7.8.4 Clinical Laboratory Evaluations

Except urinalysis performed only at baseline visit (visit 1), hematology and blood chemistry will be assessed at baseline visit (visit 1), visits 2, 3, 4, 5, 6, 7, 8, 9, 10, 12 and 3-weekly visits during the maintenance phase treatment and follow-up. Laboratory assessments included the following:

- Hematology: WBC count with differential, absolute neutrophil count (ANC), red blood cell (RBC) count, hemoglobin, hematocrit, platelet count, prothrombin time (PT)/partial thromboplastin time (PTT) and international normalized ratio (INR)
- Clinical chemistry (or local panel if inclusive of the following): sodium, chloride, potassium, glucose, blood urea nitrogen (BUN), creatinine, calcium, aspartate aminotransferase (AST)/SGOT, alanine aminotransferase (ALT)/SGPT, total bilirubin, alkaline phosphatase, lactic acid dehydrogenase (LDH), total protein, albumin
- Urinalysis (baseline only): protein, glucose, blood, leukocytes, nitrites, urobilinogen, bilirubin, pH, specific gravity, ketones
- Thyroid function (Screening, Day 84 and every 3 months during the follow-up): T3, T4 and TSH

All local laboratory data will be stored in the database with the units in which they are originally reported. Laboratory data in summary tables and patient data listings will be presented in the international system of units (SI Units). Laboratory data not reported in SI units will be converted to SI units before further processing or data analysis.

Summary statistics (mean, median, standard deviation, and range) of laboratory values for hematology tests and chemistry tests and their changes from baseline values will be tabulated for each visit, by treatment arm. Baseline is defined as the last value prior to first dosing.

Laboratory tests will be graded using NCI-CTCAE v4.03 toxicity grading (see Appendix 1).

Worst change from baseline in toxicity grade for selected laboratory parameters will be presented in shift tables: in each treatment arm, the patient's baseline grade will be cross-

tabulated by the patient's maximum post-baseline grade during the treatment. Data from scheduled and unscheduled visits will be used for finding maximum post-baseline NCI-CTCAE grade of laboratory values.

All laboratory measurements will be presented in a listing.

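### The arms number their visits differently, so the SAP's atezolizumab completion count up to visit 12 and its by-visit safety tables compare different study days if programmed as written

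*SAP*

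**What the plan says.** SAP 7.3 states that "Patient disposition information will be summarized by treatment group and in total for ITT set", and one item in its list is the "Number of patients receive all doses of atezolizumab up to visit 12 based on dose administration page". No study day and no arm-specific visit is attached to it.

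Footnote a to each SAP schedule shows where the fixed-day visits end. For the combination arm (Table 1): "A window of ±3 days is permitted for Visits 3 through 12". For control (Table 2): "A window of ±3 days is permitted for Visits 3 through 9". In both tables the last fixed-day column is Day 105 (Week 15). After that, control is seen every 3 weeks, and its open-ended visits begin at Visit 10 ("Follow-up phase visits (Visits 10+) will be permitted a window of"). In the combination arm they begin at Visit 13 ("Follow-up phase visits (Visits 13+) will be permitted a window of").

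SAP 7.8.4 gives one laboratory list for both arms, in which "hematology and blood chemistry will be assessed at baseline visit (visit 1), visits 2, 3, 4, 5, 6, 7, 8, 9, 10, 12", followed by a clause adding the 3-weekly maintenance visits. Laboratory summaries "will be tabulated for each visit, by treatment arm". SAP 7.8.5 does the same for vital signs, and SAP 7.8.9 summarises ECOG by visit. Neither document maps visit numbers across the arms.

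**The concern.** Atezolizumab is the background treatment in both arms. A reader asking whether adding CMB305 changed its delivery needs both arms measured over the same period. If visit 12 is taken from each arm's own schedule, control is held to a longer run of doses, and two arms with the same delivery would show different completion.

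The by-visit safety tables have a related problem. A row labelled with one visit number would hold values from different study days and different points in the atezolizumab course. Safety by arm is a secondary objective, so these tables will be read comparatively even though no hypothesis is tested.

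**Working it through.** The plan states no figure for this point, so the check is a mapping of visits to days followed by an illustration of size.

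**Visit-to-day map.** Days to 105 are read from SAP Tables 1 and 2. Control Visits 10 to 12 are inferred from Visit 9 = Day 105 plus 3-week steps: 105 + 21 = 126, 126 + 21 = 147, 147 + 21 = 168.

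| Visit | Combination day | Control day | Difference |
|---|---|---|---|
| 2 | 0 | 0 | 0 |
| 3 | 14 | 21 | 7 |
| 4 | 21 | 42 | 21 |
| 5 | 28 | 63 | 35 |
| 6 | 42 | 70 | 28 |
| 7 | 56 | 84 | 28 |
| 8 | 63 | 98 | 35 |
| 9 | 70 | 105 | 35 |
| 10 | 84 | 126 | 42 |
| 11 | 98 | 147 | 49 |
| 12 | 105 | 168 | 63 |

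From Visit 3 to Visit 12 no visit number falls on the same day in both arms.

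**Scheduled infusions through visit 12.** Combination: Days 0, 21, 42, 63, 84, 105 = 6. Control: the same six plus Days 126, 147, 168 = 9.

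**Direction.** Every control patient with all 9 infusions also has the first 6. Counting to Day 168 therefore gives a number no larger than counting to Day 105.

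**Size, under an assumption.** Suppose time to stopping is exponential and identical in the arms, and that a patient still on treatment has had every dose. The fraction on treatment at day d is 2^(−(d/30.4375)/median). Day 105 is 3.450 months and Day 168 is 5.520 months. As a check on the formula, the plan's medians of 3 and 5.2 months give 6-month rates of 2^(−6/3) = 0.250 and 2^(−6/5.2) = 0.449, which match its 25% and 45%.

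| Median (months) | Day 105 | Day 168 | Gap (points) | Patients of 40 |
|---|---|---|---|---|
| 3 | 45.1% | 27.9% | 17 | 18 vs 11 |
| 5.2 | 63.1% | 47.9% | 15 | 25 vs 19 |
| 12 | 81.9% | 72.7% | 9 | 33 vs 29 |
| 24 | 90.5% | 85.3% | 5 | 36 vs 34 |

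The 12- and 24-month rows are added to show the range; they are not planning values. With both arms cut at the Week 15 visit, each has 6 scheduled infusions and the gap is zero on every row.

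**By-visit tables.** Visit 3 pairs Day 14 with Day 21, and Visit 10 pairs Day 84 with Day 126. The single visit list in SAP 7.8.4 follows Table 1: under control numbering, Visits 6 (Day 70) and 8 (Day 98) carry no safety laboratory draw, so those control laboratory cells would be empty.

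**Separate point: worst grade.** SAP 7.8.4 takes the maximum post-baseline grade during treatment. Scheduled post-dose draws to Day 105 are 9 in the combination arm (Days 14, 21, 28, 42, 56, 63, 70, 84, 105) and 5 in control (Days 21, 42, 63, 84, 105). Assume a 5% chance of a transient abnormality per draw, independent between draws. The chance of at least one is then 1 − 0.95^9 = 37% against 1 − 0.95^5 = 23%. Both arms are 3-weekly afterwards, so a patient treated to about one year has 21 against 17 draws, giving 66% against 58%.

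**The case against.** The strongest reply is that visit 12 is plainly a combination-arm label. The protocol uses it as a landmark for CMB305 delays (Sections 5.6 and 7.2.2), and the neighbouring items in SAP 7.3 concern CMB305. The authors probably meant Week 15. The table shells and dataset specifications are separate documents not available here and may already key rows by day. Control Visit 12 is not printed in Table 2. Its nominal Day 168 is an inference, and it can move with the ±4-day window and the one-week delay allowed after Day 105 (Protocol 8.2.3.2). All of this stands. It lowers the chance that the count will be wrong, but it does not supply the missing anchor, and SAP Section 8 makes the SAP text prevail over the protocol.

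A reader might infer three stronger things that the documents do not support:

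- That atezolizumab delivery cannot be compared at all. SAP 7.8.3 reports doses given, cumulative dose, treatment duration in weeks and compliance by arm, none of it by visit number.
- That control will show a 17-point deficit. That figure needs a 3-month median and stopping at progression, whereas Protocol 6.3 allows treatment to continue past progression under conditions.
- That SAP 7.8.4 leaves out control laboratory data at Visit 11 (Day 147). Its 3-weekly maintenance clause covers them, because control enters maintenance after Day 84.

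The worst-grade asymmetry comes from the visit schedules, not the numbering. It dilutes with longer treatment, and independence between a patient's serial draws is only an assumption.

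**Conclusion.** The concern holds as a misaligned descriptive comparison. Followed literally, SAP 7.3 sets 6 scheduled infusions against 9, which can only leave control completion equal or lower when delivery is the same. The size is about 5 to 17 points for exponential medians of 24 to 3 months, and it rests on an assumed stopping curve common to both arms. The by-visit safety tables mix study days from Visit 3 onward, and that bias has no fixed direction.

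It does not reach the primary results: OS and PFS are computed from dates, between-arm comparisons are declared exploratory, and no decision rule uses the affected outputs. It is worth correcting before the tables are programmed.

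**What to change.** In SAP 7.3, replace the visit 12 limit on the atezolizumab count with: through the Week 15 dosing visit (nominal Day 105, within the visit window), which is Visit 12 in the combination arm and Visit 9 in control. Tie it to the visit and not to a hard Day 105 cut, because Protocol 7.2 allows atezolizumab up to 3 days either side and a hard cut would drop infusions given on Days 106 to 108.

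In SAP 7.8.4, 7.8.5 and 7.8.9, tabulate by nominal study day or week and compare arms only on days that both schedules share. For laboratory values these are Days 0, 21, 42, 63, 84 and 105, then 3-weekly. Vital signs and ECOG also share Days 70 and 98. State the laboratory visit list in 7.8.4 separately for each arm.

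Optionally, and as a separate matter, add a worst-grade shift table restricted to the shared laboratory days beside the all-data table. It leaves out some combination-arm draws, which the all-data table still shows.

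The cost is SAP and table-shell wording, plus one extra table if the option is taken. No new data are needed, and treatment and visit schedules do not change.

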# 7.4 **Protocol Deviations**

The clinical study team will define CSR reportable protocol deviation and major protocol deviation to be excluded from efficacy evaluable set. They clinical team will have quarterly review of all potential CSR reportable and major protocol deviations during study conduct and prior to database lock. CSR reportable and major protocol deviations will be categorized by deviation type.

A listing will be provided for all protocol deviations.

# 7.5 Demographic and Baseline Characteristics

Demographics, cancer history and tumor specific therapy history will be summarized by treatment arm for the ITT and safety analysis set. Demographics, cancer history, medical history and tumor specific therapy history will be presented in a data listing for all patients in ITT Analysis Set.

Baseline demographic and baseline characteristics summary will include the following:

- Age in years, calculated as integer part of (date of informed consent date of birth + 1)/365.25.
- Age categories of (>= 70 years, >= 80 years)
- Sex (Male and Female) and Childbearing Potential status for Female
- Race
- Ethnicity
- Height (cm) at baseline, defined as the last non-missing value prior to first dosing.
- Weight (kg) at baseline, defined as last non-missing value prior to first dosing
- ECOG Performance Status at baseline, defined as last non-missing value prior to first dosing
- Number of Target/Non-Target Lesions at Baseline
- Number of Target Lesions at Baseline
- Number of Non-Target Lesions at Baseline
- Sum of Target Lesion Diameters at Baseline (mm)

Cancer History summary will include the following:

- Type of Sarcoma (Myxoid/Round Cell Liposarcoma and Synovial Sarcoma)
- Time from diagnosis (Month), calculated as (first dosing date date of diagnosis + 1) /30.4375. In case of partial date, "15" is used for missing day, "Jun" is used for missing month.
- Stage at Diagnosis
- Disease Status at Study Start
- Soft Tissue Sarcoma Grade at Diagnosis
- Current Tumor Staging (Stage T, Stage N, Stage M and Stage TNM)
- NY-ESO-1 Expression (%) and categories of NY-ESO-1 (1%-25%, >25% 50%, >50% 75%, >75% 100%)
- Progression Status at Screening

Medical and surgical history includes diagnosis or surgery entered on the medical and surgical history form.

Prior tumor specific therapy history includes therapy/treatment entered on the prior anti-cancer therapy form. The summary will include the following:

- Any prior therapy
- Type of therapy (Radiotherapy, Immunotherapy, Chemotherapy, Other Therapy)
- Number of lines of prior therapy (1, 2, >=3). Line of therapy will be assigned and reviewed by medical team at several milestone time points.
- Number of prior chemotherapy agents
- Frequency and percentage by prior chemotherapy agents
- Best response of prior chemotherapy
- Reason for discontinuation from prior chemotherapy

# 7.6 Efficacy Analyses

The efficacy analysis will be performed based on ITT set and supportive analysis will be performed based on Efficacy set and subgroup of ITT and efficacy set.

# 7.6.1 Analysis of Primary Efficacy Variables

# 7.6.1.1 Progression-Free Survival (PFS) and Overall Survival (OS)

PFS and OS analyses by treatment arm using Kaplan-Meier methodology based on the ITT set will be performed. Median with 95% CIs by treatment arm will be provided by treatment arm. The Kaplan-Meier plots will be displayed. The SAS code used to calculate the median (and 95% CI) and create the Kaplan-Meier plot is listed in Appendix 2.

As an exploratory analysis, PFS and OS between CMB305+atezolizumab arm vs. atezolizumab alone arm for all ITT patients will be compared. Hazard ratio, its corresponding 95% confidence interval (CI), and p-value (based on a 2-sided stratified log-rank test) from a Cox proportional hazards model stratified by disease type will be presented. Unstratified analysis will also be performed to estimate the hazard ratio and the corresponding 95% CIs and p-values. Since the sample size is not based upon a hypothesis to be tested regarding the differences in PFS between treatment arms, the statistical analyses to compare PFS and OS differences between treatment arms should be considered exploratory.

Exploratory analyses of OS at 6, 12, 18, and 24 months, and PFS at 3 and 12 months will also be assessed. The survival rate estimates between the two treatment arms will be compared using the following:

Z= difference in x-month survival rates / square root of sum of variance

where variance=square of survival standard error from Product Limit Estimate from SAS PROC LIFETEST, assuming independence of the two treatment arms, and the survival standard error for x-month is the same as the survival standard error at the event time prior to x-month if x-month is not an event time.

A forest plot of hazard ratios and their two-sided 95% confidence intervals will be presented for the subgroups defined in section 7.7 of this document, based on the ITT analysis set. The interaction p-value from Cox proportional hazards model will be also shown in the plot.

Progression-free survival and overall survival data will be presented in data listing.

